- o intubation and mechanical ventilation
- $\circ~$ confirmed sepsis (positive blood or urine cultures) up to post-natal discharge
- o total number of nights in hospital
- Gestational hypertension (GH)
- Birth at <32 weeks, <34 weeks and <37 weeks
 - o Spontaneous
 - latrogenic for PE, GH or FGR
 - o latrogenic for other reason
- Death of one twin and / or both twins before discharge from hospital
 - $\circ~$ Miscarriage of the whole pregnancy or death of one twin <24 weeks' gestation.
 - Stillbirth or neonatal death of one or both twins at <32 weeks, <34 weeks, <37 weeks and at any gestation.
- $\circ~$ Birthweight <3rd, <5th and <10th percentile for gestational age.
- Placental abruption (clinically or on placental examination) at <32 weeks, <34 weeks, <37 weeks and at any gestation.
- Postpartum hemorrhage (defined as blood loss ≥1 L within the first 24 hours after birth).
- Neonatal morbidity
 - Intraventricular hemorrhage (IVH) grade II or above Defined as bleeding into the ventricles
 - Grade II (moderate) IVH occupies <50% of the lateral ventricle volume
 - Grade III (severe) IVH occupies ≥50% of the lateral ventricle volume
 - Grade IV (severe) Hemorrhagic infarction in periventricular white matter ipsilateral to a large IVH
 - Neonatal sepsis confirmed bacteremia in cultures
 - Encephalopathy grade (mild, moderate, severe)
 - Neonatal seizures
 - $\circ~$ Anemia defined as low hemoglobin and / or hematocrit requiring blood transfusion
 - $\circ~$ Respiratory distress syndrome defined as need of ventilation with or without surfactant
 - \circ $\;$ Necrotizing enterocolitis requiring surgical intervention $\;$
 - $\circ~$ Composite of any of the above
- Neonatal therapy
 - \circ $\,$ Neonatal intensive care unit admission $\,$
 - Ventilation defined as need of positive pressure (continuous positive airway pressure (CPAP) or nasal continuous positive airway pressure (NCPAP)) or intubation
 - Composite of any of the above
- \circ $\$ Length of stay in neonatal intensive care unit

Birth weight percentile for gestational age at delivery will be calculated using the Fetal Medicine Foundation birthweight chart (Nicolaides et al., 2019).

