6.7 Sample size

The sample-size calculation presented here is based on detecting a treatment effect that produces a 50% reduction in the incidence of preterm PE from an anticipated 5.5% in the placebo group to 2.75% in the aspirin group. A total sample of 2,200 participants has 90% power of detecting this difference at a (two-tailed) significance level of 5%. Allowing for 9% attrition, it will be necessary to randomise a total of 2,400 pregnancies. On the assumption that 60% of women with twin pregnancies fulfilling the entry criteria agree to participate in the study, we would need to approach 4,000 such women.

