6.9 Assignment of intervention

Sequence generation: Randomisation will be by random permuted blocks and participants will be stratified by centre and chorionicity. The treatment allocation will only be revealed to the researchers after completion of the study or where clinically essential.

Allocation concealment mechanism: Each treatment pack will only be identified by a kit code. When a participant enrols onto the study, the randomisation system will assign participants two kit codes corresponding to the treatment arm to which they have been assigned. If IMP is being dispensed from a pharmacy, the participant or a member of the clinical team, on behalf of the participant, will bring the prescription with the allocated kit codes detailed to the pharmacy, where the pharmacy will provide her with the bottles matched to the kit codes. Neither the pharmacy at each clinical site or the clinical staff will have access to the codes, except in case of an emergency.

Allocation Implementation: Responsibility for who is enrolled in the trial and receives IMP is the Principal Investigator's (PI). S/he makes his/her eligibility decision according to the approved protocol. Other physicians, employed at the same Clinical Site may enrol participants as long as they appear on the Trial Delegation log and are signed off by the PI.

Blinding

RenaClinical will provide labelling for the IMP bottles ensuring complete blinding of the IMP to all investigators and participants in the study. That includes the PI, participating research doctors, pharmacists at the local clinical trial pharmacy, project managers and others involved in the trial. They are all blinded to the allocation. As mentioned previously, the tablets will be identical, so it will not be possible to distinguish between the active (aspirin) and placebo. RenaClinical and Sealed Envelope will keep the kit codes confidential to maintain the blind.

Emergency unblinding

In case of emergency, the facility to unblind a participant's treatment allocation will be available at all times during the study via an online service provided by Sealed Envelope, which has a telephone unblinding backup system in cases where the hospital network is not functioning. The coordinating team will receive an email informing them a participant has been unblinded but this email will not reveal the treatment allocation.

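### The neonatal morbidity and therapy composites omit death, and NICU stay has no rule for babies who die, so a survival benefit of aspirin can make these secondary outcomes look worse

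*Protocol*

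**What the plan says.** Protocol section 6.5 (Outcomes, Secondary Outcomes) lists the neonatal items in three parts.

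- **Neonatal morbidity:** intraventricular haemorrhage of grade II or above, sepsis, encephalopathy, seizures, transfused anaemia, respiratory distress syndrome and surgical necrotising enterocolitis, then "Composite of any of the above".
- **Neonatal therapy:** NICU admission and ventilation, closed by the same line.
- **NICU stay:** "Length of stay in neonatal intensive care unit", with nothing on babies who die in the unit or never reach it.

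Death is a separate secondary outcome higher in the list: "Death of one twin and / or both twins before discharge from hospital". Miscarriage or loss of one twin before 24 weeks, and stillbirth or neonatal death by gestation, sit beneath it. The structured summary (1.3) and the objectives (5.3) also keep death out of both composites.

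The protocol does not say whether the neonatal outcomes are counted over fetuses, live births, survivors or pregnancies. Section 6.5 adds that further neonatal data come from the special care or NICU discharge summary of admitted babies. Section 6.10 promises intention-to-treat analysis.

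**The concern.** Death competes with every item in these lists. A stillborn baby cannot have sepsis or a NICU admission, and a baby who dies in the delivery room may have no listed event.

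The choice of denominator can be left to a SAP, but with the components fixed as they are, no choice removes the problem:

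- Over all fetuses, a loss without a component is scored as a non-event.
- Over live births or survivors, the comparison conditions on something that happens after randomisation and that aspirin may change.

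The direction matters because of the trial's own rationale. Section 5.1 cites larger reductions for early than for preterm preeclampsia in singletons. If aspirin works similarly in twins, averted deaths would tend to be at early gestations, where survivors are most likely to have morbidity and long stays. These outcomes would then be most distorted when treatment succeeds.

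**Working it through.** **The plan's own figure.** The protocol gives no figure for the neonatal outcomes. Its one calculation is for the primary outcome, "from an anticipated 5.5% in the placebo group to 2.75% in the aspirin group", and it reproduces. The pooled two-sided formula gives 1,097 per arm, or 2,194, against 2,200 stated; with 1,100 per arm the power is 90.1%. Adding death to secondary composites changes none of this.

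**Inputs.** All rates below are assumptions, per fetus:

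- dP, dA: death in the placebo and aspirin arms (pairs 3% v 2%, 4% v 2%, 6% v 4%)
- m: morbidity in babies who survive in either arm (8%, 15%)
- s: share of babies whose death is averted who survive with morbidity (50%, 80%, 100%)
- q: share of deaths that had a listed component first (0, 30%, 70%, 100%)

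**Formulas.** Let b = (1 − dP) × m.

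- Without death, all fetuses: placebo b + dP·q; aspirin b + (dP − dA)·s + dA·q. The difference is (dP − dA)(s − q), so apparent harm arises exactly when s exceeds q.
- Without death, survivors only: m against [b + (dP − dA)·s] / (1 − dA).
- With death, all fetuses: b + dP against b + (dP − dA)·s + dA. The difference is −(dP − dA)(1 − s), which cannot be positive in this model.

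**Worked case: dP = 4%, dA = 2%, m = 8%, s = 80%, q = 30%.** Here b = 0.96 × 0.08 = 0.0768.

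| Outcome | Placebo | Aspirin | RR |
|---|---|---|---|
| Without death, all fetuses | 0.0768 + 0.012 = 8.88% | 0.0768 + 0.016 + 0.006 = 9.88% | 1.11 |
| Without death, survivors | 8.00% | 0.0928 / 0.98 = 9.47% | 1.18 |
| With death, all fetuses | 0.0768 + 0.04 = 11.68% | 0.0768 + 0.016 + 0.02 = 11.28% | 0.97 |

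With 2,400 pregnancies split 1:1 (the ratio is not stated), each arm has 2,400 fetuses. Without death that is about 213 v 237 events; with death it is about 280 v 271. Ignoring correlation within twin pairs, the standard error of the first log RR is √(1/213 + 1/237 − 2/2,400) ≈ 0.09, giving a 95% interval of about 0.93 to 1.33. The distortion is systematic but of the order of one standard error.

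**Over the whole grid.**

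| Outcome | RR range |
|---|---|
| Without death, all fetuses | 0.91 to 1.27 |
| – of which every death has a component first (q = 100%) | 0.91 to 1.00 |
| Without death, survivors only | 1.02 to 1.24 |
| With death, all fetuses | 0.91 to 1.00 |

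**A milder case: 4% v 3%, m = 8%, s = 50%.** Without death the rates are 0.0768 + 0.04q and 0.0818 + 0.03q. At q = 0 the RR is 1.07, at q = 0.5 it is 1.00, and at q = 0.8 it is 0.97. With death it is 11.68% v 11.18%, RR 0.96.

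**NICU stay.** Assume 15% of survivors stay 14 days on average, babies who die stay 2 days, and babies whose death is averted stay 30 to 60 days. At 4% v 2%, the placebo mean per fetus is 0.96 × 0.15 × 14 + 0.04 × 2 = 2.10 days. The aspirin mean is 2.016 + 0.02 × 30 + 0.02 × 2 = 2.66 days, or 3.26 days with 60-day stays. At 3% v 2% it goes from 2.10 to 2.38 or 2.68 days. The arm with fewer deaths has the longer mean stay.

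**The case against.** A reader might infer that every baby who dies is counted as event-free. The protocol does not say so. Under section 6.5, ventilation alone meets the respiratory distress definition, sepsis, haemorrhage and seizures also count, and NICU admission alone meets the therapy composite. A baby treated before dying is usually already an event. (Section 5.3 requires surfactant and ventilation, and omits encephalopathy and seizures, so fewer would count on that wording.) The gap is confined to fetal losses, delivery-room deaths, very early deaths without a component, and stays cut short by death. This part of the objection stands.

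A reader might also infer that the composite will reverse sign. That depends on s and q, neither of which is known. The model also holds morbidity in other survivors equal between arms, although aspirin may lower it. In the milder case, suppose the 1-point fall in deaths lies within the planned 2.75-point fall in preterm preeclampsia, and treat that fall as per baby. If the other 1.75 points drop from 50% to 8% morbidity, the aspirin rate is 0.0768 + 0.005 − 0.0175 × 0.42 = 0.0745, RR 0.97, with no apparent harm. This too stands: reversal is possible, not predicted.

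Deaths are prespecified outcomes in the same list, so a mortality difference would be visible. That helps but does not settle the matter. Death-or-morbidity cannot be rebuilt from two separate totals when their overlap is unknown, and the composite will carry its own confidence interval.

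Finally, the glossary defines neonatal morbidity within the first 28 days of life, which suggests live births, and a SAP may set the denominator. True, but that choice conditions on surviving to birth.

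**Conclusion.** The point holds in limited form. Both composites are fixed without death, NICU stay has no rule for it, and no denominator repairs this. If aspirin averts deaths, these outcomes can be biased against it.

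On the assumed rates, the all-fetus morbidity RR runs from 0.91 to 1.27 without death and from 0.91 to 1.00 with it. Apparent harm appears only where averted deaths carry morbidity more often than deaths had a prior component. The mean NICU stay rises from about 2.1 to between 2.4 and 3.3 days. No rate comes from the protocol, so the ranges show a mechanism and do not forecast a result.

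The documents do not support saying that all deaths are scored as event-free, or that the trial will report harm. The primary outcome and sample size are untouched. This is a worthwhile, inexpensive improvement to secondary outcomes.

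**What to change.** Prespecify in the SAP, which section 6.10 requires to be final before the blind is broken:

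1. Death before discharge or any neonatal morbidity, and death before discharge or any neonatal therapy, reported alongside the existing composites and not replacing them.
2. All fetuses alive at randomisation as the denominator, with a live-birth version as supporting.
3. Each component, and death, reported separately.
4. For NICU stay, either rank deaths as the worst outcome, or label the result as survivors only and show it beside deaths.

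**Cost.** The data are already collected, so the work is a short SAP section and some extra tables. Death and morbidity differ in weight, which is why the components must be shown. Counting from randomisation brings in early losses unrelated to preeclampsia, which dilute the composite; the live-birth version shows how much. Editing section 6.5 itself would be a substantial amendment under section 7 (Protocol amendments), needing ethics and competent-authority approval. Adding the outcomes through the SAP leaves the section 6.5 wording as it is.

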6.7 Sample size

The sample-size calculation presented here is based on detecting a treatment effect that produces a 50% reduction in the incidence of preterm PE from an anticipated 5.5% in the placebo group to 2.75% in the aspirin group. A total sample of 2,200 participants has 90% power of detecting this difference at a (two-tailed) significance level of 5%. Allowing for 9% attrition, it will be necessary to randomise a total of 2,400 pregnancies. On the assumption that 60% of women with twin pregnancies fulfilling the entry criteria agree to participate in the study, we would need to approach 4,000 such women.

6.8 Recruitment and retention

Recruitment

In all the participating centres, all eligible women attending for their first-trimester scan will be invited to take part in the randomised controlled trial by the designated trial teams. Recruitment rates will be actively monitored by the TMG. This will include analyses by centre of the number of women invited to participate in the trial and the number randomised. Appropriate strategies will be implemented if recruitment falls below an acceptable level.

Retention

If women fail to attend their follow-up visits, the trial coordinators will contact them to arrange for another visit within 7 days.

COVID-19 Impact

The impact of COVID-19 on recruitment and retention to the trial has been considered and we believe the impact will be minimal because all on-site trial visits coincide with routine clinical visits. Should a participant test positive for COVID-19 or display symptoms consistent with a COVID-19 infection, local hospital policy on attendance at the site will be followed.

6.9 Assignment of intervention

Sequence generation: Randomisation will be by random permuted blocks and participants will be stratified by centre and chorionicity. The treatment allocation will only be revealed to the researchers after completion of the study or where clinically essential.

Allocation concealment mechanism: Each treatment pack will only be identified by a kit code. When a participant enrols onto the study, the randomisation system will assign participants two kit codes corresponding to the treatment arm to which they have been assigned. If IMP is being dispensed from a pharmacy, the participant or a member of the clinical team, on behalf of the participant, will bring the prescription with the allocated kit codes detailed to the pharmacy, where the pharmacy will provide her with the bottles matched to the kit codes. Neither the pharmacy at each clinical site or the clinical staff will have access to the codes, except in case of an emergency.

Allocation Implementation: Responsibility for who is enrolled in the trial and receives IMP is the Principal Investigator's (PI). S/he makes his/her eligibility decision according to the approved protocol. Other physicians, employed at the same Clinical Site may enrol participants as long as they appear on the Trial Delegation log and are signed off by the PI.

Blinding

RenaClinical will provide labelling for the IMP bottles ensuring complete blinding of the IMP to all investigators and participants in the study. That includes the PI, participating research doctors, pharmacists at the local clinical trial pharmacy, project managers and others involved in the trial. They are all blinded to the allocation. As mentioned previously, the tablets will be identical, so it will not be possible to distinguish between the active (aspirin) and placebo. RenaClinical and Sealed Envelope will keep the kit codes confidential to maintain the blind.

Emergency unblinding

In case of emergency, the facility to unblind a participant's treatment allocation will be available at all times during the study via an online service provided by Sealed Envelope, which has a telephone unblinding backup system in cases where the hospital network is not functioning. The coordinating team will receive an email informing them a participant has been unblinded but this email will not reveal the treatment allocation.

6.10 Data collection, management and analysis

Data collection

All of the main participant information for this study will be entered into an electronic CRF that will be printed and signed by the enrolling researcher. The CRF will be composed of 3 parts:

CRF part 1 This will include participant demographics, medical and obstetric history, measurements of MAP and UtA-PI, performance of an ultrasound scan to confirm the gestational age by the measurement

of fetal CRL of the bigger twin, eligibility criteria, and randomization details. Participants will be identified on CRFs by participant code and site name, date of enrolment and the enrolling site-PI or fellow.

CRF part 2 This will record details of the routine clinical visits (including ultrasound findings, MAP, IMP compliance and adverse events) and details of the telephone interviews.

CRF part 3 This will record details of pregnancy and postnatal outcomes.

All parts of CRFs should be signed by the site-PI and / or fellows for each participant enrolled, including those removed / withdrawn from the study for any reason. The reason for removal/withdrawal must be noted on the study conclusion CRF by the site-PI. CRFs must be kept current to reflect the participant's status at each phase during the course of the study.

The CRFs will be the source documents of the study that must be available at all times for inspection by the regulatory authorities. A participant identification record will be kept by each site-PI that would allow linking of the participant study number, participant name and date of birth for those included in the study along with participant contact information. This file will be kept electronically at sites.

Ancillary CRFs

Ancillary CRFs, including exceptions to SAEs, SAEs and study exit forms will be available within the Sealed Envelope/Red Pill system. These should be completed, as required. If an SAE form is completed, the participating site must also email FFIS/FMF immediately following completion of the eCRF to alert them that an SAE form has been submitted so that a clinical review can be completed.

Non-adherence and non-retention

For non-adherers (as defined by poor attendance to clinical visits) we will record details of pregnancy and postnatal outcomes as for adherers. Reasons for non-adherence and non-retention and those lost to follow up will be recorded in the CRF.

Data management

The Chief Investigators will act as custodian for the trial data. The following guidelines will be strictly adhered to:

- Participant data will be pseudo-anonymised.
- All pseudo-anonymised data will be stored on GDPR-compliant servers and/or a password-protected computer.

Statistical methods

Statistical analysis plan: A stand-alone Statistical Analysis Plan (SAP) detailing the analysis will be produced before follow up is complete. To ensure that the analysis can be validated and is reproducible, this document will include listings of all program code used for the statistical analysis together with sample outputs, tables and figures. The SAP may be informed by analyses of data blinded to treatment, but it will be finalised before the blind is broken. The SAP will be approved by the IDMC and by the TSC.

Results will be reported according to the CONSORT statement (Moher et al., 2001). It is envisaged that the analysis will be undertaken using R and WinBugs software.

Summary statistics will be produced for aspirin and placebo groups. Continuous data will be summarized in terms of means, standard deviations, minimum, maximum and quartiles. Attribute data will be summarised in terms of frequency counts and proportions.

Statistical analyses will be performed on an intention-to-treat basis. Logistic regression analysis will be used to determine the significance of difference in incidence of preterm-PE between the aspirin and placebo

groups, adjusting for the effect of centre (random effect) and the logistic transformation of risk. The treatment effect will be quantified as odds ratio with 95% confidence interval (CI) in the aspirin group. Homogeneity of the treatment effect will be examined by centre, chorionicity, risk group and specific maternal characteristics. Sensitivity analysis will be performed to examine the effect of withdrawal of consent and loss to follow up. Kaplan-Meier estimates of the cumulative incidence of PE by treatment group, in which deliveries without PE are treated as censored observations, will be produced. The statistical software package R will be used for data analysis. Results will be presented as 95% confidence intervals with no corrections for multiple testing.

Safety: The incidence rates of adverse events and serious adverse events and their relationship to trial drugs will be summarised by treatment group. The proportion of women discontinuing treatment will be summarised by reason and by treatment group. All investigators, participants and clinicians will be unaware of the treatment groups. All outcomes will be determined before the blind of the trial is broken.

